8.5 Test for changes in MetS-related traits

Exploratory outcomes: Changes in body mass index, waist circumference, blood pressure, HDL cholesterol, triglycerides, HbA1c, and fasting glucose levels

Although longer clinical trials involving daily consumption of EVOO and nuts have observed improvement in MetS-related traits, it is unclear if improvements in MetS-related traits will be observed after 4-weeks. As an exploratory analysis, we will test for changes in MetS-related traits before vs. after the 4-week intervention, including changes in body mass index, waist circumference, HDL cholesterol, triglycerides, HbA1c, and fasting glucose levels using a paired sample t-test.

8.6 Sample size justification

The prevalence of epigenetic age acceleration in people with metabolic syndrome is unknown. Also, it is unknown if a short term nuts and EVOO intervention will have measureable effects on estimates of epigenetic age. Thus, this pilot study will provide feasibility data necessary to estimate sample sizes for larger trials. Assuming 50 individuals and a type 1 error rate of $\alpha=0.05$, the study has 0.80 power to detect difference of 0.4 standard deviations in the difference in epigenetic age and chronological age. We acknowledge that power is a limitation of the current study, and designed the study to maximize the sample size based on budget constraints to provide prevalence and potential effect size estimates to guide power calculations when planning a future larger, longer trial.

References

3. Grundy SM: **Pre-diabetes, metabolic syndrome, and cardiovascular risk.** *J Am Coll Cardiol* 2012, **59**:635-643.
5. Grundy SM: **Metabolic syndrome update.** *Trends Cardiovasc Med* 2016, **26**:364-373.

Appendix A

NUTS and OIL CONSUMPTION DIARY

1. Make an entry in this diary every day during the study, at roughly the same time each day.
2. For each day, circle either "Yes" or "No" to indicate whether you ate the nuts and oil.
3. Return the completed assessment forms to the study staff at your visit to the clinic.
4. There is space at the bottom of the form for you to add comments (good or bad) regarding your daily consumption of the nuts and oil.
5. THANK YOU FOR BEING A PART OF THIS STUDY!

	Day 1	Day 2	Day 3	Day 4	Day 5	Day 6	Day 7
Day of Week	MON	TUE	WED	THU	FRI	SAT	SUN
Date (MM/DD)	/	/	/	/	/	/	/
.							
Did you consume a one ounce portion of nuts today?	Yes No						
Did you consume 2 tablespoons of olive oil today?	Yes No						

Adherence Diary

Comments:

Appendix B.

14-item Questionnaire of Mediterranean diet adherence

1. Do you use olive oil as your main cooking fat?

¹ Yes

² No

2. How much olive oil do you consume in a given day (including oil used for frying, salads, restaurant meals, etc.)?

	
----------------------	----------------------

tablespoons

3. How many vegetable servings do you consume per day? (1 serving is $\frac{1}{2}$ a cup of cooked vegetables or 1 cup of raw vegetables)

	
----------------------	----------------------

servings

4. How many fruit servings, including natural fruit juices, do you consume per day? (1 serving is a medium fresh fruit; $\frac{1}{2}$ cup of chopped, cooked, or canned fruit; $\frac{1}{2}$ cup of juice)

	
----------------------	----------------------

servings

5. How many servings of red meat, hamburger, or meat products (ham, sausage, etc.) do you consume per day? (1 serving is 2-3 ounces)

	
----------------------	----------------------

servings

6. How many servings of butter, margarine, or cream do you eat per day? (1 serving is 1 Tbsp.)

	
----------------------	----------------------

servings

7. How many sweet or carbonated beverages do you drink per day?

	
----------------------	----------------------

beverages

8. How much wine do you drink per week?

	
----------------------	----------------------

glasses

9. How many servings of legumes do you consume per week? (1 serving is $\frac{1}{2}$ cup of beans or lentils)

	
----------------------	----------------------

servings

10. How many serving of fish or shellfish do you consume per week? (1 serving is 2-3 ounces)

	
----------------------	----------------------

servings

11. How many times per week do you consume commercial sweets or pastries (not homemade), such as cakes, cookies, pies, or pudding?

	
----------------------	----------------------

times

12. How many servings of nuts (including peanuts) do you consume per week? (1 serving is $\frac{1}{4}$ cup of nuts or 2 tablespoons of nut butter)

	
----------------------	----------------------

servings

13. Do you preferentially consume chicken, turkey, or rabbit meat instead of veal, pork, hamburger, or sausage?

¹ Yes

² No

14. How many times per week do you consume vegetables, pasta, rice, or other dishes seasoned with sauce made with tomato and onion, leek, or garlic and simmered with olive oil?

	
----------------------	----------------------

times

Appendix C

STUDY EVALUATION

1. How often during the course of your participation in this study did you replace foods in your diet with the tree nuts and olive oil?

-2	-1	0	1	2
Never	Very Rarely	Occasionally	Very Often	Always

2. How often during the course of your participation in this study did you eat the tree nuts and olive oil in addition to the other foods in your diet?

-2	-1	0	1	2
Never	Very Rarely	Occasionally	Very Often	Always

3. On a scale of 1 to 10, how difficult did you find it to eat the tree nuts and olive oil every day?

1	2	3	4	5	6	7	8	9	10
									
NOT AT ALL DIFFICULT		MODERATELY DIFFICULT			VERY DIFFICULT				

4. On a scale of 1 to 10, how difficult did you find it to consume the olive oil every day?

1	2	3	4	5	6	7	8	9	10
									
NOT AT ALL DIFFICULT		MODERATELY DIFFICULT			VERY DIFFICULT				

5. On a scale of 1 to 10, how did eating the tree nuts and olive oil daily make you feel?

1	2	3	4	5	6	7	8	9	10
									
NOT GOOD AT ALL	NO DIFFERENCE					VERY GOOD			

6. On a scale of 1 to 10, how did consuming the olive oil daily make you feel?

1	2	3	4	5	6	7	8	9	10
									
NOT GOOD AT ALL	NO DIFFERENCE					VERY GOOD			

7. Did you use the provided recipes to help incorporate the tree nuts and olive oil into your diet?

1 Not at all	2 Not much	3 Sometimes	4 Often	5 Very often
-----------------	---------------	----------------	------------	-----------------

8. On a scale of 1 to 5 (with 5 being the very best I have tasted), how much did you like the flavor of the olive oil?

1 Did not like at all	2 Disliked somewhat	3 Neither liked or disliked	4 Liked somewhat	5 Liked a great deal
-----------------------------	---------------------------	-----------------------------------	------------------------	----------------------------

9. On a scale of 1 to 5 (with 5 being the very best I have eaten), how much did you like the walnuts?

1 Did not like at all	2 Disliked somewhat	3 Neither liked or disliked	4 Liked somewhat	5 Liked a great deal
-----------------------------	---------------------------	-----------------------------------	------------------------	----------------------------

10. On a scale of 1 to 5 (with 5 being the very best I have eaten), how much did you like the almonds?

1 Did not like at all	2 Disliked somewhat	3 Neither liked or disliked	4 Liked somewhat	5 Liked a great deal
-----------------------------	---------------------------	-----------------------------------	------------------------	----------------------------

11. On a scale of 1 to 5 (with 5 being the very best I have eaten), how much did you like the pistachios?

1 Did not like at all	2 Disliked somewhat	3 Neither liked or disliked	4 Liked somewhat	5 Liked a great deal
-----------------------------	---------------------------	-----------------------------------	------------------------	----------------------------

12. Will you continue to eat tree nuts and olive oil daily after completing the research study?

1 Very unlikely	2 Unlikely	3 Neutral	4 Somewhat likely	5 Very likely
-----------------------	---------------	--------------	-------------------------	------------------

13. Will you continue to eat olive oil daily after completing the research study?

1 Very unlikely	2 Unlikely	3 Neutral	4 Somewhat likely	5 Very likely
-----------------------	---------------	--------------	-------------------------	------------------

14. If eating tree nuts and olive oil improved your metabolic health, how likely would you be to continue to eat tree nuts and olive oil daily?

1 Very unlikely	2 Unlikely	3 Neutral	4 Somewhat likely	5 Very likely
-----------------------	---------------	--------------	-------------------------	------------------

15. If consuming olive oil improved your metabolic health, how likely would you be to continue to consume olive oil daily?

1 Very unlikely	2 Unlikely	3 Neutral	4 Somewhat likely	5 Very likely
--------------------	---------------	--------------	----------------------	------------------

16. Do you think that you would be able to participate in a study like this one that lasted 3-4 years?

In other words, would you be able to continue eating the tree nuts and olive oil for 3-4 years?

¹ Yes
² No

If no, why not?

17. Please describe any specific problems or barriers that you encountered that made it difficult for you to eat the tree nuts and olive oil each day.

18. Please describe any suggestions you have that would make eating the tree nuts and olive oil each day easier for participants in future studies.

19. Can [name] or someone she designates contact you for future studies?

1 Yes
2 No

Appendix D.

We would like to ask you some questions about epigenetic age. Epigenetic age is a DNA-based measure that predicts the biological age of your cells. Having an accelerated epigenetic age means that the biological age of your cells may be more advanced than your chronological age.

20. Using the scale below, indicate how much you want to know your epigenetic age:

[figure not shown]
1 Not at all	2 Not much	3 Neutral	4 Somewhat	5 Very much
-----------------	---------------	--------------	---------------	----------------

21. For question #1, why did you select that answer?

[figure not shown]
22. Before beginning this study, if you were told your epigenetic age appeared more advanced than your chronological age, do you think you would be more or less motivated to eat the nuts and olive oil everyday?

1 Not motivated at all	2 Less motivated	3 Neutral	4 More motivated	5 Very motivated
---------------------------	---------------------	--------------	---------------------	---------------------

[figure not shown]
23. Before beginning this study, if you were told your epigenetic age appeared younger than your chronological age, do you think you would be more or less motivated to eat the nuts and olive oil everyday?

24. If eating tree nuts and olive oil slowed biological aging, how likely would you be to continue to eat tree nuts and olive oil daily?

25. If consuming olive oil slowed biological aging, how likely would you be to continue to consume olive oil daily?

26. Do you feel we did a good job explaining the concept of epigenetic aging?

27. For question #76, can you comment on why you selected that answer?

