4.3.3 End of week 1 and week 2 telephone calls

During the end of week 1 telephone call, participants will be contacted via telephone and asked questions about their adherence, and any potential side effects observed. Participants will receive additional counseling for how to incorporate the nuts and oil into a daily meal as needed. A follow up phone call at the end of week 2 will be scheduled to assess compliance and to answer participant questions, and a final measurement visit will be scheduled for the end of week 4 for a morning time and participants will be asked to be fasting.

4.3.4 Final measurement visit, end of week 4

The same measures, as listed in the in-person screening visit will be performed. Study questionnaires, with the exception of demographics and health history, will be distributed and completed, and adherence diaries will be collected.

For participants of the intervention arm 1 (participants educated about epigenetic age acceleration), a self-administered exit questionnaire will be given to qualitatively explore participants' perception of epigenetic age, and challenges and motivators for behavior change during the intervention. The open-ended questions will be designed to ascertain understanding of epigenetic age, and assess the challenges and motivators participants encountered during the intervention.

Participants in both arms will be administered an Intervention Experience Assessment to explore how participants' experiences would impact the feasibility of a larger clinical intervention in terms of challenges and motivators.

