5.3 Questionnaires

Demographic information: Name, marital status, date of birth; racial/ethnic group; occupation; education.

Personal medical history: Select questions about the participant's medical history, past and present.

Dietary intake: Participants will be asked to complete Mediterranean Diet 14 item dietary screener.

Current medications: Prescription medications; participants will be instructed to bring medications to the clinic.

Intervention Assessments (see appendix A)

Compliance-Intake of the study foods, tree nuts and EVOO will be tracked on a daily basis using a compliance diary. The participant will record on a daily diary the following information:
Did you eat the nuts today? - Yes, No
Did you consume the oil today? -Yes, No

Telephone contacts and maintenance of the cohort: Telephone contact will be used to monitor participants for study compliance and side effects by phone at the end of week 1 and 2. During the phone call participants will be invited to ask any questions and to discuss any problems with the study, specifically their adherence to the study foods. Participants' medication history will be reviewed.

Perception of Epigenetic Age Assessment -For participants of the intervention arm 1 (participants educated about epigenetic age acceleration), a self-administered exit questionnaire will be given to qualitatively explore participants' perception of epigenetic age, and challenges and motivators for behavior change during the intervention. The questions will be designed to ascertain understanding of epigenetic age, and assess the challenges and motivators participants encountered during the intervention.

Intervention Experience Assessment- Participants in both study arms will be administered an intervention experience assessment to explore how participants' experiences would impact the feasibility of a larger clinical intervention in terms of challenges and motivators.

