8.3 Participants' perception of epigenetic age, challenges and motivators

Primary outcome 5: Perception of Epigenetic Aging Assessment and Intervention Experience Assessment

To gain preliminary data supporting the feasibility of testing epigenetic age acceleration as a motivating factor for behavior change in a larger trial, participants of the intervention arm 1 (participants educated about epigenetic age acceleration), will be given a self-administered exit questionnaire to qualitatively explore participants' perception of epigenetic age. All participants will be given a self-administered Intervention Experience Assessment to explore participant experiences in the study, and the challenges and motivators for behavior change during the intervention. The \ questions will be designed to ascertain understanding of epigenetic age, and assess the challenges and motivators participants encountered during the intervention. All participants will be asked if they can be contacted for future studies.

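### The exit questionnaire is meant to ascertain understanding of epigenetic age, but Appendix D has no direct comprehension question and prints the definition before its first item

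*Combined protocol and SAP*

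**What the plan says.** Section 8.3 names the outcome: "Primary outcome 5: Perception of Epigenetic Aging Assessment and Intervention Experience Assessment". The first of these instruments is Appendix D, given to arm 1 only. The second is Appendix C, given to everyone. Section 8.3 then gives the purpose: the "questions will be designed to ascertain understanding of epigenetic age, and assess the challenges and motivators participants encountered during the intervention". Section 4.3.4 states the same aim and adds a format: "The open-ended questions will be designed to ascertain understanding of epigenetic age". Section 5.3 repeats it: "The questions will be designed to ascertain understanding of epigenetic age".

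Appendix D begins with two sentences of explanation. The first is "Epigenetic age is a DNA-based measure that predicts the biological age of your cells". The second is "Having an accelerated epigenetic age means that the biological age of your cells may be more advanced than your chronological age". Items 20 to 27 follow. Item 22 supposes that the participant had been told of an advanced epigenetic age and asks "do you think you would be more or less motivated to eat the nuts and olive oil everyday". Item 26 asks "Do you feel we did a good job explaining the concept of epigenetic aging".

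**The concern.** Three sections promise information on understanding, and the form that should supply it does not ask for it. A participant who remembers nothing of the arm 1 education can read the two opening sentences and answer every item.

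This matters for planning the larger trial. A primary objective in Section 1.1 compares adherence between the educated and uneducated arms. If adherence does not differ, the investigators will want to know whether participants had grasped the message and were not moved by it, or had never grasped it. Those two explanations point to different next steps, and the present form gives little help in choosing between them.

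The lesser issue is item 22. Its stem asks for a comparison, but its response codes mix comparisons with absolute levels, so a given code can mean different things for different participants.

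**Working it through.** The plan gives no figure for Primary Outcome 5. The one power statement, in Section 8.6, concerns epigenetic age minus chronological age and does not bear on this point. The check is a reading of each item against the stated purpose.

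**Step 1. Items in Appendix D.** They run from 20 to 27, so 27 − 20 + 1 = 8.

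| Item | What it asks for | Evidence on understanding |
|---|---|---|
| 20 | Wish to know one's own epigenetic age | None |
| 21 | Free-text reason for a rating | Incidental only |
| 22, 23 | Motivation under a hypothetical result (older, younger) | None |
| 24, 25 | Likelihood of continuing the foods if they slowed aging | None |
| 26 | How well the study team explained the concept | A rating of the explanation |
| 27 | Free-text comment on a rating | Incidental only |

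Direct comprehension items: 0 of 8. Items that might show understanding incidentally: 2 of 8 (21 and 27). Treating item 27 as the follow-up to item 26 is an inference from its position, because the question number it cites (76) does not exist in the appendices. Item 21 likewise cites question 1, although the items start at 20.

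**Step 2. Appendix C.** It has items 1 to 19 and does not mention epigenetic age: 0 of 19.

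**Step 3. Other contacts.** Sections 4.0 and 4.3.2 describe the education as written materials with a brief explanation and describe no check of what was taken in. The week 1 and week 2 calls (Sections 4.3.3 and 5.3) cover adherence, side effects, counselling, medication and participants' questions. Appendix D is therefore the only place where understanding is to be ascertained.

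**Step 4. Order.** Both definitions come before item 20. A correct remark in item 21 or 27 could reflect the education four weeks earlier or the paragraph just read. Nothing on the form separates the two.

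**Step 5. Number of people.** With 1:1 allocation of 50, arm 1 has 50 ÷ 2 = 25. Recruitment is up to 50 and some may not reach the final visit, so 25 is an upper figure.

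**Step 6. Item 22.** Codes 1 and 5 describe a level (no motivation, high motivation). Codes 2 and 4 describe a change (less, more). Code 3 is neutral. That makes two levels, two changes and one neutral. A participant who was already keen and is unmoved by the information could reasonably choose 3, as no change, or 5, as a high level. No response scale for item 23 is visible in the text.

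**The case against.** The strongest reply is that this is a qualitative exploration in a feasibility pilot. Section 1.1 speaks of how participants perceive epigenetic age, the form is titled a perception assessment, and understanding is one phrase in its description. That stands in part: items 20 to 25 address perception and motivation, and Appendix C asks about barriers, so most of Primary Outcome 5 is served. It does not dispose of the point, because the aim of ascertaining understanding appears in three sections, including the statistical one.

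Second, a reader might infer that Appendix D yields nothing at all on understanding. The documents do not support that. Items 21 and 27 invite free text, and a comment on how well the concept was explained may reveal what was missed. What fails is direct and uncontaminated evidence.

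Third, part of the form is not visible. Missing figures may hide response scales, but the stems are all there and the numbering is unbroken from 1 to 27, so a lost comprehension item is unlikely. The objection does stand for item 23, where a fault in the anchors cannot be asserted.

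Fourth, a reader might infer that the item 22 anchors spoil a planned analysis. Section 8.3 plans no score, mean or test for that item, and many participants with no change would simply choose the neutral code. The anchors are a fault of wording that makes the codes harder to interpret, and no more than that. Nor is item 22 the main measure of motivation: the randomised adherence comparison is, since it observes behaviour.

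Fifth, a question at week 4 cannot tell never understood from understood and then forgotten. This stands. A null adherence result would also be hard to read in any case. If one assumes a 0.4 SD difference in adherence (borrowed from Section 8.6, where it refers to another quantity), 25 per arm and two-sided 0.05, power is Φ(0.4 × √(25/2) − 1.96) = Φ(1.414 − 1.960) = Φ(−0.546) ≈ 0.29.

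**Conclusion.** The point holds as a mismatch between a stated aim and the instrument. Following the plan as written cannot give direct evidence on understanding, which is a stated content of Primary Outcome 5. Because the definition is printed first, even the incidental evidence cannot be credited to the education. Item 22 is a secondary wording fault, limited to that item.

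The effect is confined to what Primary Outcome 5 can show for arm 1. Sample size, type 1 error, power and Outcomes 1 to 4 are untouched. The conclusion assumes that the visible stems are the complete form, and that the arm 1 educational material, which is not in the documents, contains no comprehension check of its own.

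It would go too far to say that Primary Outcome 5 as a whole fails, or that a repaired form would settle why education did or did not change adherence. The repaired form would show retained understanding, which is useful context for the adherence comparison but not an explanation of it.

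**What to change.** Place one open question at the start of Appendix D, before any definition: *In your own words, what does accelerated epigenetic age mean, and what does it say about health?* Move the two defining sentences to follow it. Code each answer correct, partly correct or incorrect against the arm 1 educational material, state that rule in Section 8.3, and report the result as understanding retained at week 4.

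For item 22, use change anchors throughout: *Much less motivated / Less motivated / No change / More motivated / Much more motivated*. Check the printed scale of item 23 and alter it only if it has the same mixture. Correct the question numbers cited in items 21 and 27 at the same time.

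The cost is one added question, one moved paragraph, new anchor wording and the coding of up to about 25 short answers, with no extra visit. The main drawback is timing. This version is dated 14 January 2022 and intervention visits close on 3 March 2022, so some forms may already be complete. If so, report the two versions separately and accept that each set will be small. If nearly all forms are in, state in the report that understanding was not measured directly.
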